## 8.8. Severity Assessment

GRADE	Clinical Description of Severity
0	No Change from normal or reference range (This grade is not included in the Version 4.03 CTCAE document but may be used in certain circumstances.)
1	MILD adverse event
2	MODERATE adverse event
3	SEVERE adverse event
4	LIFE-THREATENING consequences; urgent intervention indicated
5	DEATH RELATED TO adverse event

Note the distinction between the severity and the seriousness of an AE. A severe event is not necessarily an SAE. For example headache may be severe (interferes significantly with the patient's usual function) but would not be classified as serious unless it met one of the criteria for SAEs listed above.

## 8.9. Causality Assessment

The investigator's assessment of causality must be provided for all AEs (serious and non-serious); the investigator must record the causal relationship in the CRF, as appropriate, and report such an assessment in accordance with the SAE reporting requirements if applicable. An investigator's causality assessment is the determination of whether there exists a reasonable possibility that the investigational product caused or contributed to an AE; generally the facts (evidence) or arguments to suggest a causal relationship should be provided. If the investigator does not know whether or not the investigational product caused the event, then the event will be handled as "related to investigational product" for reporting purposes, as defined by the sponsor (see the section on [Reporting Requirements](#)). If the investigator's causality assessment is "unknown but not related to investigational product," this should be clearly documented on study records.

In addition, if the investigator determines that an SAE is associated with study procedures, the investigator must record this causal relationship in the source documents and CRF, as appropriate, and report such an assessment in accordance with the SAE reporting requirements, if applicable.

## 8.10. Exposure During Pregnancy

For both unapproved/unlicensed products and for marketed products, an exposure during pregnancy occurs if:

1. A female becomes, or is found to be, pregnant either while receiving or having been exposed (eg, because of treatment or environmental exposure) to the investigational product; or the female becomes or is found to be pregnant after discontinuing and/or being exposed to the investigational product;

An example of environmental exposure would be a case involving direct contact with a Pfizer product in a pregnant women (eg, a nurse reports that she is pregnant and has been exposed to chemotherapeutic products).

2. A male participant has been exposed (eg, because of treatment or environmental exposure) to the investigational product prior to or around the time of conception and/or is exposed during his partner's pregnancy.

If a study patient or study patient's partner becomes or is found to be pregnant during the study patient's treatment with the investigational product, the investigator must submit this information to the Pfizer drug safety unit on an SAE report form and an EDP supplemental form, regardless of whether an SAE has occurred. In addition, the investigator must submit information regarding environmental exposure to a Pfizer product in a pregnant woman (eg, a patient reports that she is pregnant and has been exposed to a cytotoxic product by inhalation or spillage) using the EDP supplemental form. This must be done irrespective of whether an AE has occurred and within 24 hours of awareness of the exposure. The information submitted should include the anticipated date of delivery (see below for information related to termination of pregnancy).

Follow-up is conducted to obtain general information on the pregnancy and its outcome for all EDP reports with an unknown outcome. The investigator will follow the pregnancy until completion (or until pregnancy termination) and notify Pfizer of the outcome as a follow-up to the initial EDP supplemental form. In the case of a live birth, the structural integrity of the neonate can be assessed at the time of birth. In the event of a termination, the reason(s) for the termination should be specified and, if clinically possible, the structural integrity of the terminated fetus should be assessed by gross visual inspection (unless preprocedure test findings are conclusive for a congenital anomaly and the findings are reported).

If the outcome of the pregnancy meets the criteria for an SAE (ie, ectopic pregnancy, spontaneous abortion, intrauterine fetal demise, neonatal death, or congenital anomaly [in a live-born baby, a terminated fetus, an intrauterine fetal demise or a neonatal death]), the investigator should follow the procedures for reporting SAEs.

Additional information about pregnancy outcomes that are reported as SAEs follows:

- Spontaneous abortion includes miscarriage and missed abortion;
- Neonatal deaths that occur within 1 month of birth should be reported, without regard to causality, as SAEs. In addition, infant deaths after 1 month should be reported as SAEs when the investigator assesses the infant death as related or possibly related to exposure to the investigational product.

Additional information regarding the EDP may be requested by the investigator. Further follow-up of birth outcomes will be handled on a case-by-case basis (eg, follow-up on preterm infants to identify developmental delays). In the case of paternal exposure, the investigator will provide the study patient with the Pregnant Partner Release of Information Form to deliver to his partner. The investigator must document in the source documents that

the patient was given the Pregnant Partner Release of Information Form to provide to his partner.

### **8.11. Occupational Exposure**

An occupational exposure occurs when, during the performance of job duties, a person (whether a healthcare professional or otherwise) gets in unplanned direct contact with the product, which may or may not lead to the occurrence of an AE.

An occupational exposure is reported to the drug safety unit within 24 hours of the investigator's awareness, using the SAE report form, regardless of whether there is an associated AE/SAE. Since the information does not pertain to a patient enrolled in the study, the information is not reported on a CRF; however, a copy of the completed SAE report form is maintained in the investigator site file.

### **8.12. Withdrawal Due to Adverse Events (See Also the Section on [Patient Withdrawal](#))**

Withdrawal due to AEs should be distinguished from withdrawal due to other causes, according to the definition of AE noted earlier, and recorded on the appropriate AE CRF page.

When a patient withdraws because of an SAE, the SAE must be reported in accordance with the reporting requirements defined below.

### **8.13. Eliciting Adverse Event Information**

The investigator is to report all directly observed AEs and all AEs spontaneously reported by the study patient. In addition, each study patient will be questioned about AEs.

### **8.14. Reporting Requirements**

Each AE is to be assessed to determine if it meets the criteria for SAEs. If an SAE occurs, expedited reporting will follow local and international regulations, as appropriate.

#### **8.14.1. Serious Adverse Event Reporting Requirements**

If an SAE occurs, Pfizer is to be notified within 24 hours of investigator awareness of the event. In particular, if the SAE is fatal or life-threatening, notification to Pfizer must be made immediately, irrespective of the extent of available AE information. This time frame also applies to additional new information (follow-up) on previously forwarded SAE reports as well as to the initial and follow-up reporting of EDP, exposure via breastfeeding, and occupational exposure cases.

In the rare event that the investigator does not become aware of the occurrence of an SAE immediately (eg, if an outpatient study patient initially seeks treatment elsewhere), the investigator is to report the event within 24 hours after learning of it and document the time of his or her first awareness of the AE.

For all SAEs, the investigator is obligated to pursue and provide information to Pfizer in accordance with the time frames for reporting specified above. In addition, an investigator may be requested by Pfizer to obtain specific additional follow-up information in an expedited fashion. This information collected for SAEs is more detailed than that captured on the AE CRF. In general, this will include a description of the AE in sufficient detail to allow for a complete medical assessment of the case and independent determination of possible causality. Information on other possible causes of the event, such as concomitant medications, vaccines, and/or illnesses, must be provided. In the case of a patient death, a summary of available autopsy findings must be submitted as soon as possible to Pfizer or its designated representative.

#### **8.14.2. Non-Serious Adverse Event Reporting Requirements**

All AEs will be reported on the AE page(s) of the CRF. It should be noted that the form for collection of SAE information is not the same as the AE CRF. Where the same data are collected, the forms must be completed in a consistent manner. For example, the same AE term should be used on both forms. AEs should be reported using concise medical terminology on the CRFs as well as on the form for collection of SAE information.

#### **8.14.3. Medical Device Complaint Reporting Requirements**

All medical device complaints, regardless of whether the medical device complaint is associated with an AE, will be collected on the applicable pages within the CRF. This includes potential incidents or malfunctions associated with the use of a medical device product. An incident or malfunction is an event that might have led to death or serious deterioration in health, or if it occurred again might have led to death or serious deterioration in health.

Significant medical device complaints are defined as those observations or incidences outside the expected normal operational ranges of the device (as detailed in the device specific training and instructions for use (IFU) documentation) that may have the potential to impact the correct operation of the device, administration of the drug or safety of the patient.

Pfizer is to be notified of all medical device complaints within 24 hours of the investigator's awareness of the event. Complaints will be forwarded to the device manufacturer, Ichor Medical Systems ("Ichor") (San Diego, CA) in accordance with the Quality Agreement between Pfizer and Ichor.

#### **8.14.4. Sponsor's Reporting Requirements to Regulatory Authorities**

AE reporting, including suspected unexpected serious adverse reactions, will be carried out in accordance with applicable local regulations.

## 9. DATA ANALYSIS/STATISTICAL METHODS

Detailed methodology for summary and statistical analyses of the data collected in this study will be documented in a statistical analysis plan (SAP), which will be maintained by the sponsor. This document may modify the plans outlined in the protocol; however, any major modifications of the primary endpoint definition and/or its analysis will also be reflected in a protocol amendment.

### 9.1. Analysis Sets

For safety evaluation, patients should have received at least one of the regimen components. For efficacy and pharmacodynamics evaluation, patients should have received at least one dose of all assigned components administered on Cycle 1 Day 1. For example, a patient would be included in the safety analyses if he is assigned to a cohort of AdC68  $6 \times 10^{11}$  VP in combination with tremelimumab but received only the AdC68 component. However, this patient would not be included in the efficacy **CCI** evaluation for that cohort. Patients who receive the designated investigational product of interest and have at least one post-dose drug concentration measurement will be included in the PK data analysis. Patients with major treatment deviations, defined as receiving <80% of their planned dose in the 28-day DLT observation period will not be evaluable for the MTD assessment and will be replaced as needed to permit MTD estimation.

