#### 3. Per protocol analysis set.

The per protocol (PP) analysis set includes all enrolled patients (for each indication) who receive at least one dose of all assigned regimen components administered on Cycle 1 Day 1 of study medication and who do not have major protocol deviations during the 28 days after the first vaccination.

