#### 9.5. Safety Analysis

The main analyses of DLTs will be based on the Per Protocol analysis set. Patients not meeting the criteria for inclusion in the Per Protocol Analysis set (ie, not evaluable for assessment of DLTs) will be replaced. Summaries and analyses of other safety parameters will include all patients in the Safety Analysis Set (see Section [Analysis Sets](#)).

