### 9.5.1. Analysis of Primary Endpoint

**Dose Limiting Toxicity (DLT)** is the primary endpoint of the dose escalation (Part A). The occurrence of DLTs observed in the dosing cohorts will govern the dose escalation as described in [Section 3.1.1 STUDY DESIGN](#). The properties of the statistical methods for the analyses of DLTs are described in section [Statistical Methods and Properties](#). Adverse Events constituting DLTs will be listed per dose level. The per-protocol population will be used for the DLT evaluation. A patient who had a major protocol deviation may be excluded from the per-protocol population and hence will be replaced for the DLT evaluation but will still be included in the safety population for the general safety evaluation.

**Adverse Events (AEs)** will be graded by the investigator according to the CTCAE version 4.03 and coded using the Medical Dictionary for Regulatory Activities (MedDRA). The focus of AE summaries will be on Treatment-Emergent Adverse Events, those with initial onset or increasing in severity after the first dose of study treatment. The number and percentage of patients who experienced any AE, SAE, treatment related AE, and treatment related SAE will be summarized according to worst toxicity grades. The summaries will present AEs both on the entire study period by dose and by cycle.

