5.3. Per-Protocol Analysis Set

The per protocol (PP) analysis set includes all enrolled patients (for each indication) who receive at least one dose of the assigned regimen components administered on Cycle 1 Day 1 of study medication and who do not have major protocol deviations during the 28 days after the first vaccination. Major protocol deviations will be determined before data base release.

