5.8. Protocol Deviations

Major protocol deviations will be determined on an ongoing basis per medical data review. Any major protocol deviation will prevent the patient from being included in the per-protocol population.

A full list of major protocol deviations will be compiled prior to database closure. Once the final list of major protocol deviations is determined the per-protocol population flag will be updated.

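### The DLT analysis set makes no exception for an under-dosed or protocol-deviating participant who had a DLT, and the SAP's per-protocol definition does not match the protocol's

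*Protocol*

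**What the plan says.** **Exclusion and replacement.** Protocol 9.1 covers major treatment deviations, "defined as receiving <80% of their planned dose in the 28-day DLT observation period will not be evaluable for the MTD assessment". It adds that these participants "will be replaced as needed to permit MTD estimation". Protocol 9.5 then states: "The main analyses of DLTs will be based on the Per Protocol analysis set", and "Patients not meeting the criteria for inclusion in the Per Protocol Analysis set (ie, not evaluable for assessment of DLTs) will be replaced". SAP 8.1.2 repeats both sentences. SAP 5.8 adds: "Any major protocol deviation will prevent the patient from being included in the per-protocol population".

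Protocol 9.5.1 is softer: "A patient who had a major protocol deviation may be excluded from the per-protocol population and hence will be replaced for the DLT evaluation". It also keeps such a participant in the safety population.

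**The one toxicity carve-out.** Protocol 3.1 allows replacement of a participant who withdraws before Day 29 only if the reason was not product-related toxicity. It concerns withdrawal, not under-dosing or deviations. It also lets a participant who stops close to Day 29 for a clearly unrelated reason be deemed evaluable by agreement.

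**Per-protocol definition.** The protocol's set contains enrolled patients "who receive at least one dose of all assigned regimen components administered on Cycle 1 Day 1". SAP 5.3 contains those "who receive at least one dose of the assigned regimen components administered on Cycle 1 Day 1". Both also require no major protocol deviation in the 28 days after the first vaccination. SAP 5.4 (mITT) keeps the word *all*. The SAP amendment log says the per-protocol definition was updated to match the protocol.

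**The concern.** DLT incidence is part of the primary endpoint in both parts of the study, and Protocol 9.5.1 names it the primary endpoint of Part A. A DLT analysis set normally treats a participant with a DLT as evaluable however much was given, because the event is itself the information sought. Here the exclusion rules apply regardless of outcome. If toxicity is what cut dosing short, the rule removes the event it was meant to count and puts a new participant in its place.

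The study is open label, and the deviation list is settled before database release, so exclusions can be decided with DLT status known. Protocol 9.1 reads as mandatory and 9.5.1 as discretionary, and nothing says which governs.

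The SAP wording raises a second question: who is in the denominator. Without *all* and without the 80% rule, two programmers could reach different per-protocol sets for a partly dosed participant.

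**Working it through.** **1. Reproduce the plan's figures.** Protocol Table 7 assumes escalation on 0/3 or 1/6 DLTs, so P(escalate) = (1−p)³ + 3p(1−p)⁵, where p is the true DLT rate. At p = 0.30 this is 0.343 + 0.9 × 0.16807 = 0.494 (stated 0.49). For 10% to 90% the formula gives 0.906, 0.709, 0.494, 0.309, 0.172, 0.082, 0.032, 0.009 and 0.001, matching all nine entries. The sequential figures also reproduce: 0.642 (stated 0.64) and 0.350 (stated 0.35). All of them presume that every DLT is counted.

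**2. When can under-dosing follow from a DLT?** The window is the 28 days after the first AdC68 vaccination (Protocol 3.2). On the nominal schedule the only doses in it are those of Day 1, because the next dosing day is Day 29. In Cohorts 6A to 9A the Day 1 order is AdC68, then tremelimumab, then PF-06801591. A DLT can therefore push dosing below 80% only by interrupting that sequence. Partial Day 1 dosing is foreseen: Protocol 9.1 gives the example of a patient assigned AdC68 plus tremelimumab who received AdC68 alone.

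**3. Effect of excluding under-dosed participants.** Let u1 be the probability of under-dosing given a DLT, and u0 the probability given none. The documents give neither, so both are assumed here. The rate among evaluable participants is p(1−u1) / [p(1−u1) + (1−p)(1−u0)]. At p = 0.30:

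| u1 | u0 | Evaluable DLT rate | P(escalate) |
|---|---|---|---|
| 0 | 0 | 30.0% | 0.494 |
| 0.10 | 0 | 0.27/0.97 = 27.8% | 0.539 |
| 0.20 | 0 | 0.24/0.94 = 25.5% | 0.588 |
| 0.20 | 0.05 | 0.24/0.905 = 26.5% | 0.567 |
| 0.05 | 0.05 | 0.285/0.95 = 30.0% | 0.494 |
| 0.05 | 0.20 | 0.285/0.845 = 33.7% | 0.420 |

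The bias is downward only when u1 exceeds u0. In a single cohort, 2/6 (stop) becomes 1/6 (escalate) if one DLT participant is excluded and the replacement has none.

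**4. Effect of the looser SAP wording.** Suppose a share d of the set is partly dosed, with DLT rate q (both assumed). The observed rate is (1−d)p + dq. At p = 0.30 and d = 0.10:

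- q = 0 gives 27.0% (P(escalate) 0.557).
- q = 15% gives 28.5% (0.525).
- q = 30% gives no change.
- q = 60% gives 33.0% (0.434).

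This is dilution only when q is below p, and only if the missed component is not classed as a major deviation. Protocol 9.1 calls dosing under 80% a major *treatment* deviation. The SAP neither restates that nor says whether it is a major *protocol* deviation.

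**The case against.** A reader might infer that the two problems compound, so that the DLT rate is biased low twice over. The documents do not support that. The first problem requires the under-dosed participant to leave the set and the second requires him to stay, so both cannot act on the same person. If the looser SAP wording admits a partly dosed participant with a DLT, it cures the first problem for him.

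Other points on that side also have force:

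- The under-dosing route is narrow. Several DLT criteria need persistence beyond 3, 7 or 14 days and cannot arise between Day 1 injections. In Cohorts 1A and 2A, AdC68 is the only Day 1 product.
- SAP 5.3 and 5.8 may already remove an AdC68-only participant as a major deviator, and its phrase can be read as meaning the whole assigned set.
- Nothing in the documents supports 10% to 20% under-dosing among DLT participants.
- Excluded participants' events stay in the Safety-set AE summaries, and escalation required review of all available safety data.

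A reader might also infer that past escalation decisions were wrong. Protocol 3.1.1 describes escalation as done, and neither document reports a DLT lost in this way.

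What these points leave standing is that no text retains a DLT in an excluded participant, that 9.1 and 9.5.1 differ in force, and that the SAP definition differs from the protocol it claims to match. The deviation route in SAP 5.8 is also not confined to Day 1 dosing.

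**Conclusion.** The gap is real, but its direction is conditional. As written, the rules can delete a genuine DLT from the primary DLT analysis. That lowers the rate only if exclusion is likelier among participants with a DLT. At a true rate of 30% with 10% to 20% of DLT participants and no others under-dosed, the escalation probability would be 0.54 to 0.59 rather than 0.49. Those inputs are assumptions, and other plausible values give no bias or the opposite sign.

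The SAP mismatch makes the DLT denominator ambiguous; it does not by itself show dilution. With Part A escalation complete, the remaining consequence is for the final DLT table, where a single reclassified participant among six matters.

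**What to change.** In Protocol 9.1 and 9.5 and SAP 5.3 and 5.8, define the DLT-evaluable set as:

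- every treated participant with a DLT in the existing window (28 days after the first AdC68 vaccination), regardless of dose received or deviations; plus
- participants without a DLT who received all assigned Cycle 1 Day 1 components at 80% or more of planned dose, and who either completed the window or were deemed evaluable under Protocol 3.1.

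Restore *all* and the 80% rule in SAP 5.3, and reconcile 9.1 with 9.5.1 so that exclusion is either mandatory or discretionary. Produce the final DLT table on this set, and list every excluded or replaced participant who had an event meeting DLT criteria.

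The cost is a few sentences in each document and one listing. The reported DLT rate may rise slightly, because under-dosed participants with a DLT stay in while those without one do not. With 5% under-dosing in both groups and a true rate of 30%, it would be 0.30 / (0.30 + 0.70 × 0.95) = 31.1%. That is a small error in the cautious direction.

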#### 1. Safety analysis set.

The safety analysis set includes all enrolled patients who receive at least one dose of one of the components of the regimen.

